
To compare the efficacy of baricitinib 4-mg + TCS, baricitinib 2-mg + TCS, or baricitinib 1-mg + TCS to placebo + TCS in AD during the double-blind placebo-controlled treatment period as assessed by patient-reported outcome measures
	
 • Percent change from baseline in Itch NRS at Weeks 52, 24, 16, 4, and 1 • Proportion of patients achieving a 4-point improvement in Itch NRS at 24 weeks • Mean change from baseline in the total score of the POEM at 16 weeks • Mean change from baseline in the PGI-S-AD scores at 16 weeks • Mean change from baseline in HADS total scores at 16 weeks • Mean change from baseline in the DLQI total scores at 16 weeks • Mean change from baseline in the WPAI-AD total scores at 16 weeks • Mean change from baseline in the EQ-5D-5L total scores at 16 weeks

Substudy: Randomized Downtitration These are prespecified objectives that will be not be adjusted for multiplicity
	

All Patients Entering the Substudy To evaluate the change in clinical response after treatment downtitration from baricitinib
 
 • 4-mg to 2-mg compared with patients who are rerandomized to remain on baricitinib 4-mg • 2-mg to 1-mg compared with patients randomized to remain on baricitinib 2-mg 
Patients Entering the Substudy with IGA 0 or 1 To evaluate the change in clinical response after treatment downtitration from baricitinib
 
 • 4-mg to 2-mg compared with patients who are rerandomized to remain on baricitinib 4-mg • 2-mg to 1-mg compared with patients randomized to remain on baricitinib 2-mg 	
 • Proportion of patients with a response of IGA 0, 1, or 2 assessed at 16 weeks after rerandomization (Week 68) and Week 104 • Proportion of patients with a response of IGA 0 or 1 assessed at 16 weeks after rerandomization (Week 68) and Week 104 • Proportion of patients with a response of EASI75 from baseline assessed at 16 weeks after rerandomization (Week 68) and Week 104 • Time to retreatment (time to IGA \geq3)

Patients Not Entered into Substudy These are prespecified objectives that will not be adjusted for multiplicity
	

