5.1. Overall Design

Study I4V-MC-JAIN (JAIN) is a Phase 3, multicenter, double-blind, randomized, placebo-controlled study evaluating the safety and efficacy of baricitinib 1-mg QD, 2-mg QD, and 4-mg QD in combination with TCS in patients with moderate-to-severe atopic dermatitis (AD) who have experienced failure of cyclosporine, or are intolerant to, or have a contraindication to, cyclosporine. The study is divided into 5 periods: a 5-week Screening period, a 1-year Double-Blind Treatment period (Week 0 through Week 52), a 1-year double-blind, long-term extension (Week 52 through Week 104) that includes a randomized downtitration substudy, a bridging extension that may last up to 96 weeks (Week 104 to up to Week 200) and a 4-week Post-Treatment Follow-Up period.

Approximately 500 patients ≥ 18 years of age will be randomized at a 1:1:2:1 ratio to receive placebo QD, baricitinib 1-mg QD, baricitinib 2-mg QD, or baricitinib 4-mg QD (100 patients in the placebo group; 100 patients each in the baricitinib 1-mg and 4-mg groups; and 200 patients in the baricitinib 2-mg treatment group). Patients will be stratified at randomization according to disease severity (Investigator's Global Assessment [IGA] 3 versus 4) and geographic region if the planned country allocation justifies.

All procedures to be conducted during the study, including timing of all procedures, are indicated in the Schedule of Activities (Section 2). Section 9.4.4 describes collection of laboratory samples; [Appendix 2](#), [Appendix 4](#), and [Appendix 5](#) list the specific laboratory tests that will be performed for this study. Study governance considerations are described in detail in [Appendix 3](#). Section 10.3.7.1 outlines information regarding the data monitoring committee (DMC) and interim analyses.

[Figure JAIN.1](#) illustrates the study design.

Abbreviations: AD = atopic dermatitis; eGFR = estimated glomerular filtration rate; ET = early termination; IGA = Investigator’s Global Assessment; IP = investigational product; PPD = purified protein derivative; QD = once daily; TB = tuberculosis; TCS = topical corticosteroids; V = visit; W = week.

^a Applicable to patients taking topical treatments (excluding emollients) or systemic treatments for AD at the time of screening.

^b Maximum dose of baricitinib for patients with renal impairment (defined as eGFR <60 mL/min/1.73 m²) will be 2-mg QD.

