5.1.3. Period 3: Double-Blind, Long-Term Extension

Patients who complete the study through Week 52 will progress into the double-blind long-term extension phase through Week 104 (Visit 22). Daily diary collection will continue through Week 68 (Visit 18) of Period 3.

Concomitant use of background TCS therapy will continue during this treatment period as described in Section 7.7.2.

5.1.3.1. Randomized Downtitration Substudy at Week 52

At Week 52, all patients will be evaluated for substudy eligibility. To be eligible, a patient must meet all of the following criteria:

- have an IGA 0, 1 (Responder) or 2 (Partial responder) at Week 52
- have not used high- or ultra-high potency TCS in the last 14 days (potency classification in [Appendix 7](#))
- do not currently have study drug interrupted
- have been assigned to baricitinib 2-mg or 4-mg at baseline (assessed by interactive web-response system [IWRS])

Treatment

Treatment in the substudy is illustrated in [Figure JAIN.1](#). Patients eligible for the substudy will be rerandomized at a 1:1 ratio at Week 52 based on the baricitinib treatment group assigned at baseline:

- 4-mg QD rerandomized to baricitinib 4-mg QD, or baricitinib 2-mg QD
- 2-mg QD rerandomized to baricitinib 2-mg QD, or baricitinib 1-mg QD

Note: Intensification of emollients and TCS may be continued or initiated to control worsening and unacceptable symptoms of AD any time during this treatment period. For management of TCS, follow the guidelines in [Section 7.7.2](#).

Retreatment

During the substudy, if worsening of AD symptoms occurs such that IGA increases to ≥ 3 , the patient will be automatically retreated with their presubstudy baricitinib dose. When the IGA is ≥ 3 , the investigator should reinstate background TCS therapy (e.g., triamcinolone 0.1% cream and/or hydrocortisone 2.5% ointment), provided the patients are not currently using TCS, and may prescribe high- or ultra-high-potency TCS following the guidelines for use of Rescue Therapies ([Section 7.7.5](#) [Rescue Therapy]). An unscheduled visit may be needed to assess worsening of symptoms and to perform clinical safety and efficacy assessments immediately before retreatment.

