5.1.3.2. Patients Not Eligible for the Substudy

Beginning at Week 52,

- Patients with an IGA ≥ 3 who
 - are in the baricitinib 2-mg, 1-mg, and placebo treatment groups will be automatically rerandomized at a 1:1 ratio to baricitinib 2-mg QD or baricitinib 4-mg QD.

- are in the baricitinib 4-mg treatment group will remain on 4-mg QD (see “Rescue during Period 3” Section 7.7.5.2).
- Patients with an IGA 0, 1, or 2 who
 - are in the baricitinib 4-mg or 2-mg treatment groups and who are not eligible for the substudy (i.e., have study drug interrupted at Week 52, or have received high- or ultra-high potency TCS in the previous 14 days), or are in the placebo or baricitinib 1-mg groups will continue in their current treatment group.
 - Patients who experience a worsening of symptoms of AD such that IGA increases to ≥ 3 will be rerandomized at a 1:1 ratio to baricitinib 2-mg QD or baricitinib 4-mg QD. Patients in the baricitinib 4-mg group will remain on 4-mg.

This option for rescue is only available once for each patient and will be assigned by IWRS; investigators will remain blinded to treatment assignments. The investigator may reinstate background TCS therapy (e.g., triamcinolone 0.1% cream and/or hydrocortisone 2.5% ointment), provided the patients are not currently using TCS, and may prescribe high- or ultra-high-potency TCS following the guidelines for use of rescue therapies (see Section 7.7.5).

Once a patient has an IGA ≥ 3 in Period 3, the investigator will know that a patient is on the highest dose of baricitinib that he/she will receive in the study; therefore, if AD symptoms remain unacceptable then discontinuation should be considered.

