7.2.2. Dose Adjustment for Renal Impairment

The rationale of dose adjustment for patients with documented renal impairment (defined as screening eGFR ≥ 40 to < 60 mL/min/1.73 m²) is detailed in Section [5.5.1](#).

The dose adjustment for renal impairment will be managed by IWRS to ensure maintenance of the treatment blind. The eGFR value from the screening visit (Visit 1) will be entered into IWRS at Visit 2, and IWRS will assign the treatment doses accordingly.

Patients with documented renal impairment (defined as screening eGFR ≥ 40 to < 60 mL/min/1.73 m²), who are randomized to the 4-mg active treatment arm will receive a dose of 2-mg QD by the IWRS. For patients randomized to the 2-mg dose or 1-mg dose, there will be no dose adjustment based on renal function.

No dose adjustment will be made for patients with screening eGFR ≥ 60 mL/min/1.73 m². These patients who are randomized to active treatment will receive their assigned dose, either baricitinib 4-mg, 2-mg, or 1-mg, respectively.

During the study, for patients with documented renal impairment when the subsequent eGFR falls < 30 mL/min/1.73 m², investigational product will be withheld until their eGFR becomes ≥ 40 mL/min/1.73 m², whereupon the investigational product dosing may resume. For patients with screening eGFR ≥ 60 mL/min/1.73 m², when the subsequent eGFR falls to < 40 mL/min/1.73 m², investigational product will be withheld until their eGFR becomes ≥ 50 mL/min/1.73 m², whereupon the investigational product dosing may resume (Section [8.1.1](#)).

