The time period for safety analysis of the 24-week interim analysis will be following criteria whichever occurs first:

- up to last dose plus up to 30 days in the study
- the first dose in Period 3
- up to dose change or up to the data cutoff date

The time period for safety analysis of the 52-week interim analysis will be following criteria whichever occurs first:

- up to last dose plus up to 30 days in the study
- the study discontinuation date
- up to dose change
- the first dose date in Period 3

**The time period for safety analysis of the 104 interim analysis** will be following criteria whichever occurs first:

- up to last dose plus up to 30 days in the study
- the study discontinuation date
- up to dose change date due to rescue

- up to dose change date due to retreatment
- the first dose in Period 4
- up to the data cutoff date

**The time period for safety analysis of the final analysis** will be following criteria whichever occurs first:

- up to last dose plus 30 days or up to last date in the study
- the study discontinuation date
- up to dose change

**Long-Term Extension (LTE) Substudy Population:** The LTE Substudy Population is defined as the patients who received at least one study medication in Period 3 of Study JAIN, and entered the downtitration substudy. Additionally, those patients who did not met study discontinuation criteria in Period 3 and continued in Period 4 will be considered in the analysis set.

**Long-Term Extension(LTE) Substudy Relapse Population:** for a subset of patients in the LTE Substudy Population defined as above who experienced a relapse in Period 3 or Period 4 (IGA $\geq$ 3 after Week 52).

**Long-Term Extension(LTE) Non-responder Population:** The LTE Non-responder Population is defined as the patients who received at least one study medication in Period 3 of Study JAIN, and IGA $\geq$ 3 at Week 52. Additionally, those patients who did not met study discontinuation criteria in Period 3 and continued in Period 4 will be considered in the analysis set.

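### Patients assigned to 4-mg with screening eGFR 40 to <60 already take 2-mg, yet the SAP counts them in the 4-mg/4-mg versus 4-mg/2-mg down-titration summary; the effect is probably small and a supportive table would remove it

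*Protocol*

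**What the plan says.** **Dosing.** Under Protocol 7.2.2, patients with screening eGFR 40 to <60 "who are randomized to the 4-mg active treatment arm will receive a dose of 2-mg QD by the IWRS". In the same section: "For patients randomized to the 2-mg dose or 1-mg dose, there will be no dose adjustment based on renal function". Note a to Table JAIN.3 repeats the reduction for the 4-mg group. Note b to Figure JAIN.1 (Protocol 5.1, repeated in SAP 5) is worded as a ceiling, "Maximum dose of baricitinib for patients with renal impairment", set at 2 mg and not limited to Period 2.

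**Substudy entry and re-randomisation.** Protocol 5.1.3.1 requires patients to "have been assigned to baricitinib 2-mg or 4-mg at baseline". None of its four eligibility criteria concerns renal function. Re-randomisation follows the baseline group: "4-mg QD rerandomized to baricitinib 4-mg QD, or baricitinib 2-mg QD". SAP 5.1 stratifies it by Week 52 IGA only. A patient whose IGA reaches 3 or more goes back to the pre-substudy dose.

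**Objective and analysis.** Protocol Section 4 (Table JAIN.2) states the contrast as "4-mg to 2-mg compared with patients who are rerandomized to remain on baricitinib 4-mg". SAP 6.2.1 takes into the LTE Substudy Population everyone who "received at least one study medication in Period 3 of Study JAIN, and entered the downtitration substudy". Table JAIN.6.3 labels them Bari 4-mg/4-mg or Bari 4-mg/2-mg, with Bari 4-mg/2-mg/4-mg after relapse. Neither that table nor Table JAIN.6.9 sets renally impaired patients apart. SAP 6.14 plans a renal subgroup only for Period 2, at Week 16, against placebo. SAP 6.2.2.3 makes Periods 3 and 4 descriptive, without inferential tests.

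**The concern.** The substudy asks whether response can be held on a lower dose. A patient who was on 2 mg before Week 52 and is on 2 mg afterwards carries no information on that question. Such a patient in the 4-mg/2-mg group is reported as down-titrated although the dose did not fall. One in the 4-mg/4-mg group is reported as having stayed on 4 mg.

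The two groups then look more alike, on average, than they would among patients whose dose really changed. That is the direction that favours down-titration. Retreatment has the same problem: the pre-substudy dose for these patients is 2 mg, so a response within 16 weeks of retreatment would be credited to a dose restoration that did not occur. Because nothing is tested in Periods 3 and 4, the point estimates and the Kaplan-Meier display are the substudy's whole output, so what the labels mean is worth getting right.

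**Working it through.** **The plan's own figure.** The only sizing figure is power above 90% for EASI75 at Week 16 (Protocol 10.1, SAP 6.1): 20% versus 45%, two-sided alpha 0.025, z = 2.241.
- 4-mg versus placebo, 100:100. Pooled rate 0.325. Null SE = √(0.325 × 0.675 × 2/100) = 0.0662. Alternative SE = √((0.16 + 0.2475)/100) = 0.0638. (0.25 − 2.241 × 0.0662)/0.0638 = 1.59, so power is 94.4%.
- 2-mg versus placebo, 200:100. The same calculation gives 98.6%.

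The stated power holds. No sizing is given for the substudy.

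**Tracing one patient: assigned 4-mg, screening eGFR 40 to <60.**

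| Stage | Reported as | Dose if the 2-mg cap applies |
|---|---|---|
| Period 2 | 4-mg | 2 mg (stated in 7.2.2) |
| Substudy, stay | Bari 4-mg/4-mg | 2 mg (inferred from note b) |
| Substudy, step down | Bari 4-mg/2-mg | 2 mg (no adjustment of the 2-mg dose) |
| Retreatment | back to 4-mg | 2 mg (pre-substudy dose) |

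**Size.** Let d be the true loss of response in patients whose dose changes, and r the share of affected patients among 4-mg substudy entrants. Their own contrast is 0, so the expected difference is (1 − r) × d + r × 0 = (1 − r)d, and the shrinkage is r × d. The documents give neither r nor d; both are assumed here.

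For scale, assume that 50 of the 100 patients planned for the 4-mg group enter the substudy (25 per arm) and that response is 80% versus 60%. The SE of the difference is √((0.8 × 0.2 + 0.6 × 0.4)/25) = √0.016, or 12.6 points.

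| r | Affected patients expected among 50 | Expected difference, d = 20 | Shrinkage | Shrinkage/SE |
|---|---|---|---|---|
| 2% | 1 | 19.6 | 0.4 | 0.03 |
| 5% | 2.5 | 19.0 | 1.0 | 0.08 |
| 10% | 5 | 18.0 | 2.0 | 0.16 |

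At r = 2%, 5% and 10% the shrinkage is 0.2, 0.5 and 1.0 points for d = 10, and 0.6, 1.5 and 3.0 points for d = 30. With 15 to 30 patients per arm the SE runs from 16.3 down to 11.5 points.

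The 2-mg to 1-mg contrast is not touched, because neither dose is adjusted for renal function.

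**The case against.** **Dosing at Week 52 is inferred.** Protocol 7.2.2 describes entry of the screening eGFR into the IWRS at Visit 2. No section says what the IWRS does at re-randomisation, and 5.1.3.1 read literally names 4-mg. A reader might infer that the substudy certainly compares 2 mg with 2 mg; the documents do not go that far. The labelling problem does not depend on this, though. A renal patient in 4-mg/2-mg has had no reduction on either reading, and one in 4-mg/4-mg has either stayed on 2 mg or moved to 4 mg against note b.

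**The reduced dose is how the protocol delivers the 4-mg assignment.** Protocol 5.5.1 chooses it so that exposure does not exceed that of 4 mg with eGFR ≥60, and Protocol 10.2 analyses patients as assigned. This stands for the 4-mg/4-mg label and is a good reason to keep the as-randomised table as the main one. It does not rescue the 4-mg/2-mg label.

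**Direction holds only in expectation.** With a handful of affected patients and no renal stratum, chance imbalance can push either way. For illustration, take 25 per arm at 80% versus 60%, with two affected patients who respond at 40%, both in the 4-mg/2-mg arm. That arm's expected rate is (23 × 0.6 + 2 × 0.4)/25 = 58.4%, a difference of 21.6 points, above the true 20. Nor does the (1 − r) factor carry over to time to relapse, which the SAP summarises in the relapse population.

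**Partly visible already.** SAP 6.6.2 lists renal status as a baseline characteristic, and SAP 6.6 summarises such characteristics for the LTE populations at the final analysis. The share could therefore be read off, but no analysis uses it.

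**Nonresponders.** Those in the placebo, 1-mg and 2-mg groups "will be automatically rerandomized at a 1:1 ratio to baricitinib 2-mg QD or baricitinib 4-mg QD", and under the cap the renally impaired among them would also take 2 mg either way. A reader might infer that a 4-mg versus 2-mg comparison is diluted there too. The SAP names no such contrast; it only lists descriptive columns by pathway.

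**Conclusion.** The point holds as a minor one. If the 2-mg cap applies at Week 52, the descriptive 4-mg/4-mg versus 4-mg/2-mg difference contains patients with no dose change in either arm and is shrunk, in expectation, by (1 − r). For an assumed loss of 20 points that is 0.4 to 2 points over r = 2% to 10%, well inside the sampling error of a small substudy. Inclusion criterion [6] admits patients with increased susceptibility to cyclosporine-induced renal damage, so r cannot be taken as zero. It gives no frequency either, so a large r is not supported.

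A reader might go on to conclude that a formal result is biased or that the main efficacy comparison is compromised. Neither follows: Periods 3 and 4 carry no test and no multiplicity control, and the Week 16 comparison with placebo is not at issue.

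**What to change.** - **Main table:** keep the as-randomised 4-mg/4-mg and 4-mg/2-mg summaries.
- **Counts:** report the number of patients with screening eGFR 40 to <60 in each substudy arm. Use the screening value, because that is the one entered into the IWRS.
- **Supportive summary:** add to SAP Tables JAIN.6.3 and JAIN.6.9 a descriptive summary of 4-mg/4-mg versus 4-mg/2-mg restricted to screening eGFR ≥60, covering IGA, EASI75, time to relapse and response after retreatment. List the remaining patients separately. Screening eGFR is fixed before re-randomisation, so the restriction keeps the randomised comparison.
- **Label:** mark it supplementary for data already locked at Week 104.
- **Nonresponders:** footnote the number of renally impaired patients in each re-randomised column.
- **Protocol:** Sections 5.1.3.1, 5.1.3.2 and 7.2.2 and note b to Figure JAIN.1 must be reconciled on what these patients receive from Week 52. No dose is proposed here.

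The cost is one extra small table, two footnoted counts and a few lines of SAP text, using a variable already collected.

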5.1.3.2. Patients Not Eligible for the Substudy

Beginning at Week 52,

- Patients with an IGA ≥ 3 who
 - are in the baricitinib 2-mg, 1-mg, and placebo treatment groups will be automatically rerandomized at a 1:1 ratio to baricitinib 2-mg QD or baricitinib 4-mg QD.

- are in the baricitinib 4-mg treatment group will remain on 4-mg QD (see “Rescue during Period 3” Section 7.7.5.2).
- Patients with an IGA 0, 1, or 2 who
 - are in the baricitinib 4-mg or 2-mg treatment groups and who are not eligible for the substudy (i.e., have study drug interrupted at Week 52, or have received high- or ultra-high potency TCS in the previous 14 days), or are in the placebo or baricitinib 1-mg groups will continue in their current treatment group.
 - Patients who experience a worsening of symptoms of AD such that IGA increases to ≥ 3 will be rerandomized at a 1:1 ratio to baricitinib 2-mg QD or baricitinib 4-mg QD. Patients in the baricitinib 4-mg group will remain on 4-mg.

This option for rescue is only available once for each patient and will be assigned by IWRS; investigators will remain blinded to treatment assignments. The investigator may reinstate background TCS therapy (e.g., triamcinolone 0.1% cream and/or hydrocortisone 2.5% ointment), provided the patients are not currently using TCS, and may prescribe high- or ultra-high-potency TCS following the guidelines for use of rescue therapies (see Section 7.7.5).

Once a patient has an IGA ≥ 3 in Period 3, the investigator will know that a patient is on the highest dose of baricitinib that he/she will receive in the study; therefore, if AD symptoms remain unacceptable then discontinuation should be considered.

5.1.4. Period 4: Bridging Extension

Patients who have completed Week 104 and have not met criteria for permanent discontinuation will have the possibility to remain in the trial for up to 96 additional weeks (up to Week 200).

During Period 4, patients will continue to receive the same treatment (baricitinib or placebo) they received during Period 3, and will have the same options for dose changes as Period 3 (if not already implemented in Period 3):

- Randomized Down titration substudy: the substudy will continue during Period 4. Therefore, patients who have not met the criterion for retreatment in Period 3 will have the possibility to be retreated with the baricitinib dose they received prior to the substudy if worsening of AD symptoms occurs such that IGA increases to ≥ 3 .
- Patients with an IGA 0, 1, or 2 at Week 52 and who were not eligible to the randomized downtitration, will be rerandomized at a 1:1 ratio to baricitinib 2-mg QD or baricitinib 4-mg QD if they experience a worsening of symptoms of AD such that IGA increases to ≥ 3 , unless the randomized uptitration has already occurred in Period 3. Patients in the baricitinib 4-mg group will remain on 4-mg.

5.1.5. Period 5: Post-Treatment Follow-Up

Patients who complete the study through Week 200 will have a post-treatment follow-up visit (Visit 801) approximately 28 days after the last dose of investigational product.

Patients who have received at least 1 dose of investigational product and discontinue early from the study must have an ETV, and return for the post-treatment safety follow-up visit (Visit 801) approximately 28 days after the last dose of investigational product.

Patients who have discontinued investigational product but remain in the study for more than 28 days without investigational product will have an ETV if they chose to discontinue early; however, a separate follow-up visit (Visit 801) is not required.

If a patient permanently discontinues investigational product for any reason before Week 16 (Visit 8), the patient is encouraged to remain in the study through Week 16 (Visit 8) and follow the regular visit schedule to provide the primary efficacy and safety data (See Section 5.1.3).

